### 8.4 Exploratory Analyses

Exploratory analyses will be performed for all other relevant parameters from EDI-OCT, color fundus photography, fluorescein angiography, and B-scan ultrasound.

Confidential

Internal reflectivity of tumors by A-scan ultrasound and macular changes (foveal avascular zone and vessel density) by OCTA will be summarized at each visit as a sub-study for sites with A-scan diagnostic probes and OCTA devices.

These analyses will be performed on ITT population.

#### 8.4.1 Subretinal Fluid by EDI-OCT

Shift tables presenting number and percentage of subjects with or without (presence/absence) subretinal fluid as measured by EDI-OCT in the study eye from baseline to each post-baseline visit will be produced by cohort and overall for the ITT population.

Descriptive statistics for change from baseline in central retinal thickness as measured by EDI-OCT in the study eye will be summarized for each visit by cohort and overall for the ITT population.

OCT is primary measurement for subretinal fluid.

#### 8.4.2 Orange Pigmentation on Tumor by Color Fundus Photography

Shift tables presenting number and percentage of subjects with or without (presence/absence) orange pigmentation on tumor as measured by color fundus photography in the study eye from baseline to each post-baseline visit will be produced by cohort and overall for the ITT population.

Other fundus photography assessments data, i.e. Tumor Melanosis, Greatest Basal Area, Distance From Fovea, and Distance From Nerve Edge, will be summarized. And for categorical parameters, shift tables reflecting the changes from baseline will be produced at each visit by cohort and overall for the ITT population.

#### 8.4.3 Other B-scan Ultrasound Data

Frequency distribution of Shape of Tumor (Dome, Collar button, Multi-lobe, Irregular, Flat, Other); Apical sub-retinal fluid (none, mild, moderate, significant); and Vitreous opacity (none, mild, moderate, dense, undetermined) will be tabulated for each visit by cohort and overall for the ITT population.

#### 8.4.4 Capillary Density by OCTA

Descriptive statistics of foveal avascular zone area, and vessel density in the study eye for the actual values and change from baseline values will be summarized for baseline, at week 26, 52 and week 104 visits by cohort and overall for the ITT population.

### 9 Safety Evaluation

Safety analyses will be performed by cohort and overall for the safety population.

The main safety analyses will be based on all available data regardless of additional therapy.

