8.3.3. Additional Therapy

Additional therapy with AU-011 at the maximum tolerated and feasible dose of 3 repeat doses of 80 µg each followed by two laser applications (treatment regimen) can be provided to:

- ensure that all subjects are able to receive the maximum tolerated and feasible dose, particularly for subjects that were treated with lower doses previously
- allow additional treatment regimens in subjects that have stable disease (treatment extension)
- allow retreatment in subjects that meet the protocol definition of disease progression

If the fovea is near the tumor edge, an adjustment to the laser procedure should be performed on each treatment day as outlined in section 8.2.2 and the Injection and Laser Procedure Manual. Subjects may be considered for additional therapy with AU-011 (defined above) after Visit 11 (Week 12) and only after inflammation from the previous treatment has resolved or when the inflammation is minimal and decreasing based on investigator judgement. Additional therapy with AU-011 must be approved by the Sponsor on a case-by-case basis prior to the initiation of therapy. Alternatively, also after Visit 11 (Week 12 Visit), standard of care therapy, including plaque brachytherapy, proton beam radiotherapy or enucleation may be used if the subject meets the protocol definition of disease progression or the Investigator judges that the disease is progressing per their clinical judgement for increases in tumor thickness or LBD that are less than the protocol definition of disease progression. Before additional therapy is performed, the following protocol assessments must be collected in the study eye unless otherwise noted: ETDRS BCVA (both eyes), slit lamp biomicroscopy, IOP measurement, fundoscopy, Fundus photos, EDI-OCT, B-scan ultrasound, A-scan ultrasound, OCTA (Cohorts 6 to 9 only) and a visual field examination. If these assessments have not been performed at the most recent study visit, an unscheduled visit is required to be performed to obtain these assessments.

The criteria for implementing additional therapy due to disease progression is as follows:

• An increase on B-scan ultrasound of >0.5 mm in melanoma thickness from baseline, not due to intralesional hemorrhage/inflammation

OR

• An increase on digital fundus photos of >1.0 mm in melanoma diameter from baseline, not due to intralesional hemorrhage/inflammation or pigmentary changes

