10.4. General Methodology

Since this is an exploratory study, no formal hypothesis testing will be performed. Descriptive statistics will be used to tabulate and summarize efficacy and safety outcomes. Background and demographic characteristics will be presented. Continuous variables will be summarized by descriptive statistics (sample size, mean, standard deviation, median, minimum and maximum). Discrete variables will be summarized by frequencies and percentages.

Safety assessments will be made at all study visits and both safety and tolerability will be evaluated by assessing the incidence of DLTs (as defined in Section 8.4.1), AEs and the incidence of SAEs.

AEs, SAEs, and other findings will be summarized by presenting the percentages of subjects with each event for each treatment group. When relevant, the time course of AEs will be presented.

All safety analyses will be presented by dose group and over all subjects. Safety analyses will summarize subjects by the treatment received.

The safety analysis will summarize ocular treatment-emergent AEs (TEAEs) in the study eye for all treated subjects using discrete summaries at the subject- and event-level by system organ class and preferred term. A TEAE will be defined as occurring on or after the day that treatment is initiated. An additional analysis will investigate ocular AEs for the non-study eye. Non-ocular TEAEs will be summarized using discrete summaries at the subject- and event-level by system organ class and preferred term. Treatment-related ocular and non-ocular TEAEs will be summarized similarly. Ocular and non-ocular TEAEs will also be summarized by severity or toxicity grade. Additionally, TEAEs will be summarized by treatment schedule as deemed necessary to better understand the safety profile.

The presence or absence of anti-drug antibodies will be summarized by treatment group.

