### 4.3.3 Safety Population

The Safety population will include all subjects who received at least one administration of study treatment. Subjects will be analyzed according to the treatment that they actually received.

This is the primary population for the safety analysis.

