## 4.4 Subgroup Definitions

The following subgroups are defined for additional characterization of efficacy and/or safety of AU-011:

- Subjects with documented growth (DG): defined as subjects who had any amount of documented growth on tumor thickness
- Phase 3 Eligible (Ph3 Elig): defined as subjects with entry criteria similar to planned phase 3 criteria
  - Subjects with tumor thickness of  $\geq 0.5$  mm and  $\leq 3.0$  mm on B-scan ultrasound, a largest basal diameter of  $\leq 13.0$  mm on fundus photos with an estimated tumor volume  $\leq 50$  mm^3 and tumor growth of  $\geq 0.3$  mm on tumor thickness within 2 years of screening
- Phase 3 Eligible Therapeutic Regimen at 2 cycles (Ph3 Elig TR2C)
  - Phase 3 Eligible subjects who received 2 cycles of AU-011 treatment, each cycle comprised of three weekly treatments with 80 $\mu$ g x 2 laser applications
- Phase 3 Eligible - High Risk for Vision Loss (Ph3 Elig HRVL)
  - Phase 3 Eligible subjects with tumor  $\leq 3.0$  mm from the fovea or optic disc

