## 9.3 Adverse Events

Adverse events (AEs) will be coded using the MedDRA Version 20.0 and will be graded according to the National Center Institute Common Terminology Criteria for AEs (NCI-CTCAE criteria [v4.03]). Uncoded terms will be presented under "SOC uncoded", with their reported term.

Related AEs are defined as events with a relationship to study treatment equal to 'related' or with missing relationship. All AEs related to study drug, related to injection procedure, and related to laser administration will be reported separately.

Adverse events in this section will be tabulated if they are treatment-emergent (TE). Non-TE adverse events will only be included in listing of all adverse events. Adverse events which begin on or after the day the treatment is initiated will be considered as treatment-emergent adverse events (TEAEs). Missing or partial AE start date will be estimated in order to include events in summary tables in case of doubt (see section 4.7 for more details).

Ocular TEAEs are those TEAEs reported as occurring in the eye(s).

All tabulations of adverse events will be presented by cohort, overall, and subgroups (defined in Section 4.4).

An overall summary table of AEs will present the number and percentage of subjects with at least one:

- TEAE
- Serious AE (SAE)
- Related SAE – broken out by study drug, injection procedure and laser related
- Ocular TEAE in the study eye
- Related ocular TEAE in the study eye – broken out by study drug, injection procedure and laser related
- Ocular TEAE in the fellow eye
- Related ocular TEAE in the fellow eye – broken out by study drug, injection procedure and laser related
- Non-ocular TEAE
- Related non-ocular TEAE – broken out by study drug, injection procedure and laser related
- Fatal AE

Tabulations of the number of subjects who experienced TEAEs as well as number of events will be presented by system organ class and preferred term (in descending frequency by SOC and by PT within each SOC). Subjects will only be counted once for each preferred term. In case a subject experienced the same event more than once, the event will be counted only once.

The following tabulations will be presented:

Confidential

- All TEAEs
- Ocular TEAEs in the study eye
- Related ocular TEAEs in the study eye – broken out by study drug, injection procedure and laser related. Three additional tabulations include:
  - Related to study drug and/or injection procedure and/or laser

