  - Related to study drug and/or laser
  - Related to injection procedure that are not related to study drug or laser
- Ocular TEAEs in the fellow eye
- Related ocular TEAEs in the fellow eye – broken out by study drug, injection procedure and laser related, if relevant
- Non-ocular TEAEs
- Related non-ocular TEAEs – broken out by study drug, injection procedure and laser related

In addition, tabulations of the number of subjects who experienced TEAEs as well as number of events will be presented by system organ class, preferred term and worst severity. Subjects will only be counted once for each preferred term. In case a subject experienced the same event more than once, the event with the worst severity will be counted in the summary.

The following tabulations will be presented:

- All TEAEs
- Ocular TEAEs in the study eye
- Related ocular TEAEs in the study eye – broken out by study drug, injection procedure and laser related. Three additional tabulations include:
  - Related to study drug and/or injection procedure and/or laser
  - Related to study drug and/or laser
  - Related to injection procedure that are not related to study drug or laser
- Related non-ocular TEAEs – broken out by study drug, injection procedure and laser related

Listing of all adverse events by cohort will be provided including the subject identifier, age, race, sex, reported term, preferred term, start date (Study Day of Start), stop date (Study Day of Stop), duration, TEAE (Yes/No), DLT (Yes/No), serious (Yes/No), associated eye (OD/OS/OU), severity (Mild/Moderate/Severe/Life-Threatening/Death), relationships (Related/Not Related to each of study drug, injection procedure, and laser administration), outcome, action taken. The adverse event listing will be sorted by treatment arm, subject identifier, start date, and reported term.

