### 9.6.7 Additional Therapy

Some subjects may receive additional therapies with AU-011 or standard care after Visit 11 (Week 12) if the Investigator determines that ocular melanoma has progressed and further treatment (additional therapy) is required. Number and percentage of those subjects who receive AU-011 will be summarized by original cohorts and overall. The highest established safe dose and regimen of drug and laser that was given at the time of the request will also be present.

Number and percentage of subjects receiving additional therapy other than AU-011 will be summarized by cohort and overall for the safety population. Details of the treatment administration for each individual subject will be provided in a data listing.

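### By-cohort adverse event tables have no split at additional AU-011, so an event after a later 3 × 80 µg, two-laser course would most likely be counted in the subject's original, lower-regimen column

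*SAP*

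**What the plan says.** - SAP 9 presents safety by cohort and overall, and adds: "The main safety analyses will be based on all available data regardless of additional therapy".
- SAP 9.3 gives all adverse event tables by cohort, overall and by subgroup. The treatment-emergent window is open-ended: "Adverse events which begin on or after the day the treatment is initiated will be considered as treatment-emergent adverse events (TEAEs"). It has no closing date and does not restart with a new course. For the worst-severity tables: "In case a subject experienced the same event more than once, the event with the worst severity will be counted in the summary".
- SAP 4.5.4 names Cohorts 1 to 9 by the regimen first planned, from 20 µg once with one laser application (Cohort 1) to three weekly 80 µg doses with two applications each (Cohorts 8 and 9).
- Protocol 8.3.3 allows additional AU-011 at that highest regimen after Week 12. One stated purpose is to "ensure that all subjects are able to receive the maximum tolerated and feasible dose, particularly for subjects that were treated with lower doses previously". Stable disease and progression are the others. Each case needs the sponsor's approval.
- SAP 9.6.7 reports on additional therapy as follows: "Number and percentage of those subjects who receive AU-011 will be summarized by original cohorts and overall". This concerns counts of recipients, not their adverse events. The section describes additional therapy only in the setting of progression, which is narrower than protocol 8.3.3.
- SAP 4.3.3 says of the safety population: "Subjects will be analyzed according to the treatment that they actually received". Protocol 10.4 also uses treatment received, and adds that "TEAEs will be summarized by treatment schedule as deemed necessary to better understand the safety profile".
- SAP 9.1 summarises exposure at Days 1, 8 and 15 only.

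**The concern.** The primary objective is the safety of dose levels, repeat regimens, laser applications and one or two cycles. No hypothesis is tested, so the by-cohort adverse event tables are where the report answers it. If a subject starts on a low regimen and later receives the highest one, a single column mixes the experience of both. A reader of the 20 µg single-dose column could then attribute to 20 µg an event that began only after 3 × 80 µg with six laser applications. The worst-severity tables add to this, because a worse later grade of the same event replaces the milder one seen after the first regimen.

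**Working it through.** The plan states no figure for this point, so the check is of text and then of scale.

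**1. Placement.** Four rules combine: columns are cohorts (SAP 9, 9.3); cohort labels describe the first regimen (SAP 4.5.4); all data count whatever therapy follows (SAP 9); and an event is treatment-emergent at any time from first treatment (SAP 9.3). Protocol Appendix 4 has events recorded without restriction through the 4-week visit after an additional course, and study-related events after that in Cohorts 1 to 9. Such events therefore reach the database, and the rules lead to the original column. In the table list (SAP 11.3.1, Tables 14.3.2.1 to 14.3.3.5), no adverse event table is cut at, or split by, additional AU-011 or standard of care.

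**2. Exposure of a retreated subject.** One additional course is 3 × 80 = 240 µg and 3 × 2 = 6 laser applications. Later share = 240 / (first dose total + 240) for dose, and 6 / (first laser total + 6) for laser, assuming full planned dosing.

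| Cohort | First regimen (µg; lasers) | After one course (µg; lasers) | Later share of dose | Later share of laser |
|---|---|---|---|---|
| 1 | 20; 1 | 260; 7 | 92.3% | 85.7% |
| 2 | 40; 1 | 280; 7 | 85.7% | 85.7% |
| 3 | 80; 1 | 320; 7 | 75.0% | 85.7% |
| 4 | 80; 2 | 320; 8 | 75.0% | 75.0% |
| 5 | 120; 3 | 360; 9 | 66.7% | 66.7% |
| 6 | 80; 2 | 320; 8 | 75.0% | 75.0% |
| 7 | 240; 3 | 480; 9 | 50.0% | 66.7% |

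Cohorts 8 and 9 start on the highest regimen, so a later course there does not mix a lower with a higher regimen. At the planned three per cohort, 7 × 3 = 21 of the 8 × 3 = 24 dose-escalation subjects start on less.

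**3. Effect on a column.** Take one subject whose only event follows the additional course:
- n = 3: 1/3 = 33.3% (exact 95% interval 0.8% to 90.6%) with no split, against 0/3 = 0% (0% to 70.8%) with one.
- n = 6: 1/6 = 16.7% (0.4% to 64.1%) against 0/6 = 0% (0% to 45.9%).
- Cohort 1 to 8 subtotal at 24: 1/24 = 4.2 points.

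As an illustration under assumed rates, let the event never follow the first regimen and have probability q in an additional course. The chance that a three-subject column shows it with k subjects retreated is 1 − (1 − q)^k. For q = 0.2, 0.5 and 0.8 this is 20%, 50% and 80% with k = 1, and 49%, 88% and 99% with k = 3.

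**4. Standard of care.** In Cohorts 1 to 9, protocol 10.2.3.3 limits reporting to study-related events beyond 30 days after treatment. With last planned doses on Days 1, 8 and 15, all-cause collection ends about Day 31, 38 or 45. The Week 6 and Week 8 visit rules extend it to about Day 43 and Day 57 for two and three doses. Standard of care is allowed only after the Week 12 visit (target Day 85 in SAP 11.2). These periods do not overlap unless standard of care closely follows an additional AU-011 course. In Cohorts 10 to 12 all events are collected to the last visit, so they do overlap.

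**5. Exposure summary.** Days 1, 8 and 15 leave out additional courses and the planned Cycle 2. On planned numbers, Cycle 2 is (6 + 6 + 15) × 3 = 81 of 27 × 6 = 162 administrations in Cohorts 10 to 12. The actual number would be lower, because Cohort 10 is treated only after growth and Cohorts 10 and 11 closed early.

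**The case against.** The strongest reply is that the SAP never says an adverse event after retreatment goes in the original column. SAP 9.6.7 speaks of original cohorts only for counts of recipients, and SAP 4.3.3 points to treatment received. This stands to the extent that placement is an inference. But the treatment-received wording assigns subjects, not events, and is silent on two regimens in sequence.

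A second reply is that SAP 9 speaks of main analyses, and protocol 10.4 provides for tables by treatment schedule where needed. That leaves room for a split, but the SAP lists no such table, and its record of changes from the protocol (SAP 4.9) covers only tumour response.

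Third, one subgroup is defined by regimen received: "Phase 3 Eligible subjects who received 2 cycles of AU-011 treatment, each cycle comprised of three weekly treatments" with 80 µg and two laser applications. It gets an adverse event column, but it has no time split, and it would miss a Cohort 1 subject who had a single later course.

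Fourth, Table 14.3.1.2 shows which cohorts contain retreated subjects, and the listings give onset days and additional therapies. A careful reader could separate events by hand. That is true, and no event is lost, but the report tables would not show the separation.

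A reader might also infer that radiotherapy reactions could pass for 20 or 40 µg reactions. The documents do not support that. All 20 and 40 µg columns lie in Cohorts 1 to 9, where an unrelated event at that stage would not normally be reported.

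**Conclusion.** The point holds as a gap in the primary-objective tables. The SAP's rules mix regimens within columns, and they most likely place events after the highest regimen under a lower one in Cohorts 1 to 7. One affected subject moves a column by 33.3 points at n = 3 or 16.7 at n = 6.

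The total distortion cannot be stated, because the number retreated is not given and each retreatment needs sponsor approval. The exposure shares assume one full additional course.

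A reader might infer that dose escalation was compromised. It was not: the protocol's reviews come one day to four weeks after a cohort's treatment and do not use these tables, while additional therapy can start only after Week 12. The standard-of-care part applies mainly to Cohorts 10 to 12, which have no low-dose column.

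The unequal collection of all-cause events between cohorts is a separate matter. It makes counts of unrelated events non-comparable, but it does not create the placement problem.

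**What to change.** - Keep the all-data tables.
- Add by-cohort tables of treatment-emergent events, related events and worst severity, limited to onset before the day of first additional AU-011 or standard of care. The planned Cycle 2 of Cohorts 10 to 12 does not count as additional therapy.
- Show later events in separate blocks, after additional AU-011 and after standard of care. Label them by time of onset, not cause: protocol 10.3.10 follows peri-tumoral changes to 26 weeks after a cycle, while retreatment may start after Week 12, so late effects of the first regimen can fall there.
- State in SAP 4.3.3 and 9 how events are assigned when a subject receives two regimens, and reconcile SAP 9.6.7 with protocol 8.3.3 on who may receive additional therapy.
- Extend SAP 9.1 to Cycle 2 and additional-course administrations, with cumulative dose and laser counts.
- Label the new tables as added after the first database lock (SAP 2 dates it 25 August 2021).
- Note that unrelated-event counts are not comparable between cohorts, and rely on the planned related-event tables. If a common window is used instead, disclose its imbalance: Day 1 to 31 gives 30 days after the last dose for single-dose subjects but 31 − 15 = 16 for three-dose subjects.

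The cost is SAP wording and a few tables from dates already collected. SAP 8.3 already makes a similar cut for efficacy, though only at standard of care. The downsides are small counts, the post-lock label, and one limitation: an event that starts before the cut and worsens after it keeps its recorded grade in the pre-cut table unless the worsening is a new record.

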#### 9.1 Extent of Exposure

Number and percentage of subjects administered with AU-011, who received full dose of AU-011 (Yes/No), Light activated (Yes/No), administered with first laser treatment (Yes/No, if applicable), administered with second laser treatment (Yes/No, if applicable), will be summarized at Day 1, Day 8 and Day 15 visits.

Details of the treatment administration for each individual subject will be provided in a data listing.

Confidential

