The first expansion cohort (Cohort 9) is designed to establish the preliminary efficacy of AU-011 delivered at the highest dose that is safe and well tolerated from the escalation phase of the trial. Cohort 10 is designed to provide estimates of growth rates in observation subjects and Cohort 11 is designed to demonstrate the safety and tolerability of administering two 3-week treatment cycles of AU-011. Cohort 12 is designed to evaluate the efficacy and safety of AU-011 in subjects with documented growth who are similar to the planned Phase 3 population.

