APPENDIX 4. AU-011 ADDITIONAL THERAPY AND SECOND CYCLE (COHORTS 10, 11 & 12) VISIT SCHEDULE

If the Investigator elects to give additional therapy with AU-011 as outlined in Section 8.3.3 then the following visit schedule and assessments must be performed. Similarly, the same visit schedule will be used for the second cycle of AU-011 for Cohorts 10, 11 and 12. Concomitant steroid treatment as outlined in section 8.3.1 should be administered with additional therapy or second cycle of AU-011. Prior to additional therapy and second cycle with AU-011, subjects must have provided informed consent and women of child-bearing potential must undergo a urine pregnancy test.

Subjects will be assessed for safety 24 hours after each AU-011 administration and at 2 weeks, 4 weeks, 12 weeks, and 26 weeks after completion of additional therapy with AU-011. Additional unscheduled visits may occur at the discretion of the investigator. If a protocol defined visit is scheduled to occur within 1 week of either the 4 week, 12 week or 26 week post additional therapy or second cycle follow-up visit, only one visit is required and the visit should be recorded as the protocol defined visit and all the assessments of that visit should be performed. After the 26 week post additional therapy or second cycle follow-up visit, remaining study visits will be conducted per the visit schedule in Section 10 and Appendix 1. If any post additional therapy, or second cycle follow-up visit will occur after the planned Week 104 End of Study Visit, the 26 week post additional therapy, or second cycle follow-up visit should be recorded as the Week 104 End of Study Visit.

AU-011 Additional Therapy or Second Cycle 1, 2 & 3

The following procedures will be performed:

- Informed Consent Form Amendment Review and Consent
- Vital signs
- BCVA (Both Eyes)
- Slit lamp biomicroscopy
- IOP
- Fundoscopy
- Fundus photos
- EDI-OCT
- OCTA (Cohorts 6 through 9 only)
- B-scan
- Blood sample for ADA testing (prior to AU-011 administration)
- Urine pregnancy test for women of childbearing potential (prior to first AU-011 administration)
- Administration of Light-activated AU-011 treatment

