### 3 Study Design and Objectives

#### 3.1 Study Objectives

##### 3.1.1 Primary Objective

The primary objective of this study is to evaluate the safety of IVT administration of one of 3 dose levels, repeat dose regimens and one or two laser applications of Light-activated AU-011 given in one or two treatment cycles in the treatment of subjects with small primary choroidal melanoma.

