#### 4.1.2 Visit Windows

The schedule of study assessments can be found in Appendix 11.1 of this SAP.

Missing scheduled visit will be substituted by an unscheduled or early withdrawal visit occurring within each follow-up visit window. If there are multiple unscheduled or early withdrawal visits occurring within the window, the closest one within the visit window will be used. If no unscheduled or early withdrawal visit occurred within the window, the visit will be considered as missing. The details are tabulated in Appendix 11.2.

An exception to this visit-window algorithm is the analysis of the "Last Visit". For all "Last Visit" time-point analyses, a subject's last non-missing endpoint assessment will be used for the analysis, regardless of if the visit falls within a particular visit window or not.

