## 9.2 Dose Limiting Toxicities

Dose limiting toxicity[ies] (DLT[s]) is defined as a drug-related safety event, severe enough to limit dose escalation (increase of dose or frequency of dosing) of AU-011.

Number and percentage of subjects with DLTs will be tabulated by cohort and overall for the safety population.

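### No planned SAP table isolates Cycle 2, so its delivery, acute ocular findings and recurrence relative to Cycle 1 cannot be read from the summary tables

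*SAP*

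**What the plan says.** **What the trial sets out to show.** The primary objective in SAP 3.1.1 concerns the safety of treatment "given in one or two treatment cycles". Protocol 4.6 adds that "Cohort 11 is designed to demonstrate the safety and tolerability of administering two 3-week treatment cycles of AU-011". Cohorts 10 (after growth is established), 11 and 12 are all planned to receive two cycles.

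**What is collected after Cycle 2.** Protocol Appendix 4 gives the second cycle its own schedule: "Subjects will be assessed for safety 24 hours after each AU-011 administration and at 2 weeks, 4 weeks, 12 weeks, and 26 weeks" after the last treatment. BCVA, slit lamp and IOP are done at each of these visits. ADA samples are taken at all of them except the 24-hour visits.

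**What the SAP tabulates.**
- Exposure (SAP 9.1): doses and lasers "will be summarized at Day 1, Day 8 and Day 15 visits". Beyond that, "Details of the treatment administration for each individual subject will be provided in a data listing".
- Windows (SAP 4.6 and 11.2): Day 1 is the first study treatment, and all visit windows count from it. SAP 11.1 reproduces the protocol's Appendix 1 schedule but not Appendix 4.
- Substitution (SAP 4.1.2): "Missing scheduled visit will be substituted by an unscheduled or early withdrawal visit occurring within each follow-up visit window".
- DLTs (SAP 9.2): "Number and percentage of subjects with DLTs will be tabulated by cohort and overall for the safety population".
- Adverse events (SAP 9.3): treatment-emergent means onset on or after the first treatment day. Tables are by cohort, overall and subgroup, and a repeat of the same event in a subject is counted once.
- Additional therapy (SAP 9.6.7): covers further treatment after the investigator judges that the disease has progressed. The planned second cycle is not named.

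**The concern.** The protocol makes the timing of Cycle 2 depend on inflammation left from Cycle 1. Early inflammation and pressure rise after re-treatment are therefore natural safety questions for a second cycle, and Appendix 4 collects the data to answer them. The SAP's stated exposure days and Day 1 windows have no place for those data.

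The Cohort 11 and 12 columns would show acute findings after Cycle 1 (Days 2, 8, 9, 15, 16 and 29) followed by late visits. A reader could take those columns as direct evidence that two cycles are tolerated. The tables would not state how many subjects started Cycle 2, how many received each full dose with both lasers, or in which cycle a DLT or a recurrent event arose.

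**Working it through.** The SAP gives no figure to reproduce. The check is a day count, a reading of the counting rules, and a tally of planned doses.

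**1. Inputs.** Windows from SAP 11.2: Week 12 = Days 65–113 (target 85), Week 26 = Days 155–211 (target 183), Week 39 = Days 246–302 (target 274). Days 114–154 belong to no window. Cycle 2 may start no earlier than the Week 12 visit (Protocol 6.1). Weekly spacing of the three Cycle 2 doses is assumed, as in Cycle 1.

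**2. Cycle 2 starting on day c.** Doses fall on c, c+7 and c+14; 24-hour visits on c+1, c+8 and c+15; the later visits 14, 28, 84 and 182 days after c+14. With c = 85:

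| Visit | Day | Where it lands |
|---|---|---|
| Doses 1–3 | 85, 92, 99 | Week 12 window |
| 24-hour visits | 86, 93, 100 | Week 12 window |
| 2-week | 99 + 14 = 113 | Week 12 window (last day) |
| 4-week | 99 + 28 = 127 | no window |
| 12-week | 99 + 84 = 183 | the Week 26 target day |
| 26-week | 99 + 182 = 281 | 281 − 274 = 7 days from Week 39 |

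The Week 12 window is normally filled by the scheduled Week 12 visit, so the 24-hour and 2-week findings go only to listings. Under Appendix 4, a 4-, 12- or 26-week visit within one week of a protocol visit is recorded as that protocol visit. Here the 12- and 26-week visits therefore do reach the tables.

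**3. Other starting days.**
- c = 113: the first dose is in the Week 12 window. The other six of the seven acute visits (three doses, three 24-hour, one 2-week) fall on Days 114–141, in the gap.
- c = 155: all seven fall in the Week 26 window, and the 2-week visit (155 + 28 = 183) is on its target day. If it replaced a missing Week 26 visit, a 2-week post-Cycle-2 finding would be labelled Week 26.
- c = 134 to 148: the 4-week visit (c + 42 = 176 to 190) is within 7 days of Day 183 and merges with Week 26.
- All starts from Day 85 to 183, equally weighted (an assumption): 99 × 7 = 693 acute visits. Each of the seven visits crosses the 41 gap days once, so 7 × 41 = 287 (41%) have no window. The other 406 (59%) fall in a window that the scheduled visit normally fills.

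The substitution rule admits only unscheduled or early-withdrawal visits. Appendix 4 visits are planned, so the SAP does not say whether the rule covers them.

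**4. Events.** A Cycle 2 event is treatment-emergent and enters the cohort tables. If the subject had the same preferred term in Cycle 1, the recurrence adds nothing to the subject count. The worst-severity tables would register a worse grade in Cycle 2 but not its cycle.

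**5. Planned administrations.** Assumes full planned enrolment, no DLT expansions, every planned dose given, and no additional therapy counted.
- Cohorts 1–8, three subjects each: 3 + 3 + 3 + 6 + 9 + 3 + 9 + 9 = 45.
- Cohort 9: 12 × 3 = 36.
- Cycle 1 of Cohorts 11 and 12: 6 × 3 + 15 × 3 = 63. Cycle 2 of the same: 63.
- Share without Cohort 10: 63 / (45 + 36 + 63 + 63) = 63/207 = 30%.
- If all six Cohort 10 subjects are treated, each cycle gains 18: 81 / (207 + 36) = 81/243 = 33%.

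**The case against.** The strongest reply is that the main safety analysis does not run through visit windows. Protocol 10.4 evaluates safety by the incidence of DLTs, AEs and SAEs. Those tables cover all available data (SAP 9 and 9.3), include Cycle 2 events, and are shown by cohort and for the two-cycle subgroup Ph3 Elig TR2C. For Cohorts 10–12, all adverse events are collected to the last visit. This stands. A reader might infer that the two-cycle part of the primary objective cannot be answered; the documents do not support that.

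A reader might also infer that no acute Cycle 2 finding reaches any by-visit table. That too goes further than the text. Table 14.3.5.3 (IOP increase on treatment days) and the ADA summary by timepoint (SAP 9.6.6) are not limited to Cycle 1, though neither is said to include Cycle 2. An acute visit might stand in for a missing scheduled visit, and some later visits merge with protocol visits.

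Listings hold every administration, and the AE listing gives study day of onset and a DLT flag, so the cycle can be recovered subject by subject. SAP 5.1 counts completion of study treatment, an indirect measure of Cycle 2 delivery. The study is exploratory, with no hypothesis test at stake. Protocol 10.4 also allows AE time course and TEAEs by treatment schedule where judged useful.

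These points lower the severity but do not close the gap. TR2C is confined to Phase 3 eligible subjects with growth, so it omits Cohort 11 subjects without growth. The SAP turns neither of the optional Protocol 10.4 displays into a table. SAP 9.3 also promises event counts, which might capture recurrences if the once-only rule applies to subjects alone, but those counts are not split by cycle either.

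**Conclusion.** The concern holds as a gap in presentation: no planned summary table explicitly isolates Cycle 2. Planned Cycle 2 doses have no rows in the exposure table. In normal conduct, most treatment-day, 24-hour and 2-week findings after Cycle 2 (BCVA, anterior chamber cells, vitreous haze, visit IOP) reach only listings, or would be mislabelled Week 12 or Week 26 if substituted. Event tables include Cycle 2 but do not separate it, so delivery, acute ocular findings and recurrence relative to Cycle 1 cannot be read from the tables.

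The day-by-day result is specific to a Day 85 start with weekly dosing; other starts move visits between windows and gaps. The 30% and 33% shares are planning figures for full enrolment and complete Cycle 2 delivery. Enrolment in Cohorts 10 and 11 was closed at Rev-11, Cohort 10 is treated only after growth, and some subjects may not complete Cycle 2, so the actual share may be lower.

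Severity: should fix. Left alone, the stated rules under-report exposure and obscure recurrence for a primary objective that names two cycles.

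**What to change.** 1. **SAP 9.1 and Table 14.3.1.1:** add rows for Cycle 2 doses 1, 2 and 3 (full dose, first laser, second laser), with the number who started Cycle 2 as denominator.
2. **SAP 11.2:** add Cycle 2 windows anchored on the first Cycle 2 dose and matching Appendix 4. State in SAP 4.1.2 that these visits are not substituted into the windows anchored on Day 1.
3. **By-visit tables:** present IOP (including Table 14.3.5.3), slit lamp, BCVA and ADA on those windows for Cohorts 10–12.
4. **SAP 9.2 and 9.3:** for Cohorts 10–12, tabulate TEAEs and DLTs by cycle of onset, counting a repeated preferred term once per cycle.

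SAP v5.0 followed the first database lock, so these should be labelled as added descriptive displays.

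The cost is SAP wording and programming, since the visits are already collected under Appendix 4. The downside is a few more tables with small denominators: up to 6 + 15 = 21 subjects, or 27 if all of Cohort 10 is treated.
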